8.7.2.3.2. Pregnant women

8.7.2.3.2.1. Analysis of general safety events, spontaneous abortion, stillbirth, and preterm birth following a primary series in pregnant women

The risk of general safety events, spontaneous abortion, stillbirth, and preterm birth will be compared among women who have received at least the first dose in a primary series of Pfizer-BioNTech original monovalent COVID-19 Vaccine versus those among pregnant women who have not received any COVID-19 vaccine during a concurrent time period. These analyses will include dose 1 and dose 2, as well as dose 3 if a third dose is received within 2 months of the second dose.

To minimize confounding by seasonality and maternal age, within the data from each data research partner, exposed pregnant women will be matched to unexposed pregnant women on estimated pregnancy start date (+/- 14 days), state (if feasible, or broader geographic region if not feasible), and maternal age. Propensity scores will be estimated within the matched population and incorporated into regression analysis for exposure-outcome associations (e.g., through weighting or stratification) to address confounding by other variables. The matching and propensity score estimation process will be done first for the overall population of pregnant women. The process will then be repeated for the subsets of pregnant women eligible for analyses of the different safety events of interest (e.g., pregnancies surviving beyond 20 completed weeks of pregnancy for analysis of stillbirth; live births for analysis of preterm birth).

The steps for matching and propensity score analysis are as follows.

a. Unexposed individuals will be matched on estimated pregnancy start date, state (or broader geographic region, as feasible), and maternal age to exposed individuals within each data research partner (in a ratio of at least 1:1). The matching will be done separately for the dose 1 exposed cohort, for the dose 2 exposed cohort, and for the dose 3 exposed cohort.

PFIZER CONFIDENTIAL

CT24-WI-GL02-RF02 3.0 Non-Interventional Study Protocol Template For Secondary Data Collection Study 20-May-2021 Page 94 of 120 An individual may be selected for each unexposed cohort (i.e., dose 1 unexposed, dose 2 unexposed cohort, or dose 3 unexposed cohort) only once. However, if an individual becomes vaccinated after being selected as an unexposed match, they may be eligible for the exposed cohort(s).

- b. The propensity to be vaccinated will be estimated among all matched individuals. The dependent variable for the logistic regression model will be vaccination status, and the independent variables will be baseline covariates (i.e., individual characteristics as described in Section 8.3.3). The model will combine dose 1, dose 2, and dose 3 index dates.
- c. The distribution of propensity scores in each cohort will be plotted to evaluate the comparability of the 2 exposure groups. Greater overlap of the propensity score distributions will indicate greater exchangeability.
- d. After the comparability of the treatment groups is confirmed, propensity scores will be incorporated into regression modeling for exposure-outcome associations through weighting or stratification.

Further details on the matching process and estimation of propensity scores will be described in the SAP.

8.7.2.3.2.2. Analysis of general safety events, spontaneous abortion, stillbirth, and preterm birth following third doses received more than 2 months after the second dose in pregnant women

In pregnant women who have received 2 doses in a primary series of Pfizer-BioNTech original monovalent COVID-19 Vaccine, the risk of general safety events, spontaneous abortion, stillbirth, and preterm birth will be compared among women who have received a third dose (either as an additional dose in a primary series or as a booster dose) more than 2 months after the second dose versus that among women who have not received a third dose of any COVID-19 vaccine. To minimize confounding by seasonality and maternal age, within the data from each data research partner, pregnant women in the dose 3 exposed cohort will be matched to women in the dose 3 unexposed cohort on estimated pregnancy start date (+/- 14 days), state (if feasible, or broader geographic region if not feasible), maternal age, and time since receipt of dose 2. Propensity score estimation will be conducted following a similar process as that for the primary series analysis of general safety events, spontaneous abortion, stillbirth, and preterm birth in pregnant women (as described in Section 8.7.2.3.2.1). As with the primary series analysis, propensity scores will be estimated within the matched population of dose 3 exposed and dose 3 unexposed individuals and incorporated into regression analysis for exposure-outcome associations (e.g., through weighting or stratification) to address confounding by other variables. The matching and propensity score estimation process will be conducted first for the overall population of pregnant women. The process will then be repeated for the subsets of pregnant women eligible for analyses of the different safety events of interest (e.g., pregnancies surviving beyond 20 completed weeks of pregnancy for analysis of stillbirth; live births for analysis of

PFIZER CONFIDENTIAL

CT24-WI-GL02-RF02 3.0 Non-Interventional Study Protocol Template For Secondary Data Collection Study 20-May-2021 Page 95 of 120 preterm birth and small size for gestational age; and live births that can be linked to infants for analysis of major congenital malformations). Further details on the matching process and estimation of propensity scores will be described in the SAP.

8.7.2.3.2.3. Analysis of birth outcomes following receipt of at least 1 dose in pregnant women

Analysis of major congenital malformations and small size for gestational age will compare singleton birth prevalence in infants born to pregnant women who have received at least 1 dose of Pfizer-BioNTech original monovalent COVID-19 Vaccine during the outcome-specific exposure window to women with singleton pregnancies who have not received any COVID-19 vaccine during the outcome-specific exposure window.

To minimize confounding by seasonality and maternal age, within the data from each data research partner, pregnant women in the exposed cohort will be matched to women in the unexposed cohort on estimated pregnancy start date (+/- 14 days), state (if feasible, or broader geographic region if not feasible), and maternal age. Propensity score estimation will be conducted following a similar process as for the primary series analysis of general safety events, spontaneous abortion, stillbirth, and preterm birth (as described in Section 8.7.2.3.2.1). Details on the matching process and estimation of propensity scores will be described in the SAP.

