8.2.3. Safety analysis in pregnant women

To be eligible for analysis of the pregnant population, women must have been pregnant for at least 1 day during the study period (regardless of the timing of estimated pregnancy start relative to the study start date) and had a pregnancy outcome (e.g., live birth, stillbirth, spontaneous abortion, ectopic pregnancy) recorded in the data sources during the study period. Pregnant women will be required to be continuously enrolled in their health plan from 12 months before the index date (as defined in Table 4 in Section 8.2.3.1, Table 5 in Section 8.2.3.2, and Table 6 in Section 8.2.3.3) until the end of pregnancy. An algorithmic approach (to be described in the SAP) will be used to identify pregnancies via their outcomes (e.g., live birth, stillbirth, spontaneous abortion, termination, ectopic pregnancy) in women of reproductive age. The algorithm will use diagnosis and/or procedure codes to identify the final pregnancy outcome of each pregnancy episode as well as the pregnancy start and end dates.

In pregnant women, safety events assessed in the general population (see Table 8 in Section 8.3.2.1 for list of outcomes), as well as pregnancy safety outcomes (spontaneous abortion, stillbirth, preterm birth, major congenital malformations, and small size for gestational age), will be assessed.

The eligible populations and exposure windows for analyses in pregnant women differ by safety event and are listed in Table 3. Only Pfizer-BioNTech original monovalent COVID-19 Vaccine doses administered during the exposure windows will be considered for inclusion in the exposed cohorts. Women who were vaccinated outside the exposure window (e.g., women who were pregnant during the study period but who were vaccinated after they gave birth) will not contribute to the exposed cohorts but may contribute unexposed person-time. Women with Pfizer-BioNTech original monovalent COVID-19 Vaccine administrations within 4 weeks before the estimated pregnancy start will be considered for inclusion in the exposed cohorts because of the imprecision of estimating pregnancy start date in claims data and because this period may be of etiologic interest for some of these safety events. If published validation studies suggesting that gestational algorithms are precise become available before the start of the study, the start of the exposure window may be redefined to be closer to pregnancy start (to be documented in the SAP).

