Table 3.	Eligible populations and exposure windows for analyses of pregnant
	women

Event	Eligible population	Exposure window
General safety events ^a	All eligible pregnancies	4 weeks before estimated pregnancy start to end of pregnancy
Pregnancy safety outco	omes	
Spontaneous abortion	All eligible pregnancies	4 weeks before estimated pregnancy start to end of pregnancy or 19-6/7 weeks of gestation, whichever is earlier
Stillbirth	All eligible pregnancies	4 weeks before estimated pregnancy start to end of pregnancy
Preterm birth	All eligible pregnancies	4 weeks before estimated pregnancy start to end of pregnancy or 36-6/7 weeks of gestation, whichever is earlier
Major congenital malformations	Singleton live deliveries with linkage to infant data available	4 weeks before estimated pregnancy start to 13-6/7 weeks of gestation (end of first trimester)
Small size for gestational age	Singleton live deliveries with linkage to infant data available	4 weeks before estimated pregnancy start to end of pregnancy

a. Safety events of interest listed in Table 8 in Section 8.3.2.1.

Analyses of major congenital malformations and small size for gestational age will require pregnancies to be linked to infants who have health plan enrollment from birth until age 3 months (or from birth until death if the infant dies before age 3 months). Where available, the Sentinel mother-infant linkage table (see Section 8.4) included in the most recently approved ETL (Extract, Transform, Load) at the time of the data extraction will be used for this study. Mother-infant linkage algorithms differ by data source and may use subscriber identification numbers and/or names and addresses; these algorithms will be described in the SAP.

8.2.3.1. Primary series analyses of general safety events, spontaneous abortion, stillbirth, and preterm birth in pregnant women

Cohort definitions for primary series analyses of general safety events, spontaneous abortion, stillbirth, and preterm birth are presented in Table 4. The primary series analysis will include dose 1, dose 2, and dose 3 if a third dose is received within 2 months of the second dose. Similar to the analytic approach in the general population, separate cohorts will be formed for each dose of Pfizer-BioNTech original monovalent COVID-19 Vaccine to assess these

PFIZER CONFIDENTIAL

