8.7.2.2. Measures of association

For comparative analyses of general safety events, Cox models or Poisson regression will be used to estimate RRs and 95% CIs within the matched cohorts. For pregnancy outcomes, hazard ratios and 95% CIs will be estimated using Fine-Gray subdistribution proportional hazards models (using gestational age as the time scale) to account for competing risks of other end-of-pregnancy events (e.g., termination, stillbirth) (Fine JP and Gray RJ, 1999).

For comparative analysis of small size for gestational age and major congenital malformations, modified Poisson regression (Zou, 2004) will be used to estimate prevalence ratios and 95% CIs within the matched cohorts.

For the dose 1 comparative risk estimation for general safety events and pregnancy outcomes, when a second dose of vaccine is administered before the risk interval following dose 1 is complete, the risk interval will be truncated at the time of dose 2, and FU after dose 2 will be excluded from the dose 1 risk estimation. In this situation, for the dose 2 comparative risk estimation, the risk interval will start on the date of the second vaccine dose and will extend for the duration of the risk interval for dose 2.

Similarly, for dose 2 comparative risk estimation for general safety events and pregnancy outcomes, when a third dose of vaccine is administered before the risk interval following dose 2 is complete, the risk interval will be truncated at the time of dose 3, and FU after dose 3 will be excluded from the dose 2 estimation. In this situation, for the dose 3 comparative risk estimation, the risk interval will start on the date of the third vaccine dose and will extend for the duration of the risk interval for dose 3.

For comparative analysis of outcomes identified separately in dose 1, dose 2, and dose 3 cohorts, comparative risks will be estimated separately by dose number. If comparative risk estimates are similar for dose 1, dose 2, and dose 3, then data from the dose 1 exposed/dose 1 unexposed cohorts, the dose 2 exposed/dose 2 unexposed cohorts, and the dose 3 exposed/dose 3 unexposed cohorts will be combined to obtain comparative risk estimates associated with at least 1 dose of the vaccine.

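### Sections 8.7.2.3.2.1 and 8.7.2.3.2.2 repeat matching among 20-week survivors (stillbirth) and live births (preterm birth), contradicting Table 3, the Table 7 follow-up start and the competing-risk model

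*Protocol*

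**What the plan says.** Protocol Section 8.2.3 gives Table 3 the governing role: "The eligible populations and exposure windows for analyses in pregnant women differ by safety event and are listed in Table 3". In that table the entry for both stillbirth and preterm birth is "All eligible pregnancies". Only major congenital malformations and small size for gestational age are limited to singleton live deliveries linked to infant data. Section 8.2.3.2 carries the Table 3 populations over to the third-dose analysis.

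Table 7 (Section 8.2.4) starts follow-up for both outcomes on the day after the index date, or at estimated pregnancy start if the index date is earlier. It sets no 20-week entry point. Section 8.7.2.2 analyses pregnancy outcomes with a Fine-Gray model on the gestational-age scale "to account for competing risks of other end-of-pregnancy events", and names termination and stillbirth as examples.

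Section 8.7.2.3.2.1 (primary series) first matches in the overall pregnant population and then adds: "The process will then be repeated for the subsets of pregnant women eligible for analyses of the different safety events of interest". The examples it gives are "pregnancies surviving beyond 20 completed weeks of pregnancy for analysis of stillbirth; live births for analysis of preterm birth". Section 8.7.2.3.2.2 (third doses) repeats this, with "pregnancies surviving beyond 20 completed weeks of pregnancy for analysis of stillbirth; live births for analysis of" preterm birth and small size for gestational age.

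**The concern.** Two parts of the current text name different cohorts for the same estimates. Propensity scores are estimated within the matched population and then carried into the outcome regression by weighting or stratification. The set that is matched is therefore the set that is analysed. A programmer working from Table 3 and one working from Section 8.7.2.3.2 would analyse different women.

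The difference matters because the exposure window opens 4 weeks before pregnancy start, so many index dates fall well before 20 weeks. Requiring a pregnancy to reach 20 weeks, or to end in live birth, then selects on something that happens after vaccination. If vaccination changed the risk of earlier loss, in either direction, the survivors in the two groups would no longer be comparable, even if they were perfectly matched at the index date. For preterm birth, a live-birth cohort contains no losses, stillbirths or terminations, so the competing-risk model has no competing pregnancy endings left to handle.

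**Working it through.** The plan gives no figure on this point, so there is nothing to reproduce. The check compares the passages, followed by an illustration on assumed inputs.

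**1. The two specifications**

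| Item | Tables 3 and 7, Section 8.7.2.2 | Sections 8.7.2.3.2.1 and 8.7.2.3.2.2 |
|---|---|---|
| Stillbirth cohort | every eligible pregnancy | pregnancies that pass 20 weeks |
| Preterm-birth cohort | every eligible pregnancy | live births |
| Start of follow-up | day after index, or pregnancy start | not restated, but entry depends on later survival |
| Other pregnancy endings | competing events | excluded for preterm birth; earlier losses excluded for stillbirth |

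The conflict is between passages of current text. As background only, the Version 4.0 entry in Section 4 gives avoidance of selection bias as the reason for widening Table 3. It lists Sections 8.2.3 and 8.2.4 for that change, not 8.7.2.3.2.

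**2. When the restriction conditions on the future**

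- Preterm birth: whether a pregnancy ends in live birth is known only after the index date, so the restriction always conditions on a post-index event.
- Stillbirth: the exposure window runs to the end of pregnancy, and the outcome is defined from 20 weeks onward. For an index date before 20 weeks the restriction selects on later survival. For an index date after 20 weeks it removes nobody. Within 20-week survivors, live birth still competes with stillbirth, so the Fine-Gray model keeps a role there.

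**3. Preterm birth, all inputs assumed**

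10% of pregnancies are frail (40% loss; 30% preterm if live-born) and 90% robust (10% loss; 8% preterm). Vaccination raises loss in frail pregnancies to 60% and has no effect on preterm birth within either stratum.

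- Preterm, exposed: 0.1×0.4×0.3 + 0.9×0.9×0.08 = 0.0120 + 0.0648 = 0.0768
- Preterm, unexposed: 0.1×0.6×0.3 + 0.0648 = 0.0180 + 0.0648 = 0.0828
- Live births: 0.04 + 0.81 = 0.85 exposed; 0.06 + 0.81 = 0.87 unexposed
- Ratio among live births: (0.0768/0.85)/(0.0828/0.87) = 9.04%/9.52% = 0.95
- Ratio among all pregnancies: 0.0768/0.0828 = 0.93

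**4. Stillbirth, all inputs assumed, index before 20 weeks**

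Let f be the frail share, L the loss before 20 weeks and S the stillbirth risk among survivors (frail, robust). Let r be the effect of vaccination on early loss, with no effect on S. In each arm, frail survivors are a = f(1 − r·L_frail), robust survivors are b = (1 − f)(1 − r·L_robust), and stillbirths are a·S_frail + b·S_robust, with r = 1 in the unexposed. The survivor ratio divides stillbirths by a + b; the all-pregnancies ratio does not.

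- Set A: f = 0.1, L = 0.50 and 0.08, S = 0.03 and 0.004
- Set B: f = 0.2, L = 0.40 and 0.06, S = 0.015 and 0.004

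| r | A: survivors | A: all | B: survivors | B: all |
|---|---|---|---|---|
| 1.0 | 1.00 | 1.00 | 1.00 | 1.00 |
| 1.2 | 0.95 | 0.93 | 0.97 | 0.94 |
| 1.5 | 0.88 | 0.81 | 0.92 | 0.86 |
| 0.8 | 1.05 | 1.07 | 1.03 | 1.06 |

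These are ratios of cumulative risks, not Fine-Gray hazard ratios. They show only that the two cohorts give different answers once early loss differs between groups, and the same answer when it does not.

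**The case against.** The strongest defence is that the survivor and live-birth wording appears only as examples, while Section 8.2.3 says where eligibility is defined. The listed matching and modelling steps contain no survival restriction, and both sections leave the details of matching to the SAP. On that reading Table 3 governs and the examples are merely loose.

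This makes the repair editorial but does not remove the conflict. The examples name exactly the two outcomes for which Table 3 says otherwise, and they are presented as the women eligible for those analyses. An SAP can add detail to a protocol, but here it would first have to choose between two protocol statements.

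Three stronger readings are tempting, and the document supports none of them.

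- A reader might infer that survivor selection manufactures an apparent benefit which the Table 3 cohort would remove. On the same assumed inputs the Table 3 cohort gives 0.93, further from 1 than 0.95, because extra loss also lowers preterm incidence when loss is a competing event. The all-pregnancies ratio is a total effect from the index date, to be read beside the spontaneous-abortion result. The survivor ratio answers a different question and mixes in selection.
- A reader might infer that every stillbirth comparison is affected. Only index dates before 20 weeks are.
- A reader might take 0.95 as the expected bias. Every input behind it is assumed.

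It is also fair to say that aligning these sections leaves other post-index conditions in place. Section 8.2.3 still requires enrollment to the end of pregnancy and a recorded pregnancy outcome.

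**Conclusion.** The contradiction stands, in both the primary-series and third-dose sections. For preterm birth the live-birth restriction always conditions on a post-index event and removes the competing losses. For stillbirth the 20-week restriction conditions on post-index survival only when the index date precedes 20 weeks.

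The size and direction of any resulting bias cannot be derived from the protocol. It is nil if vaccination does not affect earlier loss (for preterm birth, any ending other than live birth). With assumed early-loss ratios of 0.8 to 1.5, the stillbirth survivor ratio ran from 0.88 to 1.05 and the all-pregnancies ratio from 0.81 to 1.07, with no vaccine effect on stillbirth within either stratum. The case for change is that the protocol must name one cohort per estimate, and that the cohort in Table 3 agrees with the stated follow-up and model. It is not that a particular bias has been shown. This should be settled before the final analysis.

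**What to change.** In Sections 8.7.2.3.2.1 and 8.7.2.3.2.2, replace only the stillbirth and preterm-birth examples. State that matching and propensity-score estimation for these outcomes use the Table 3 populations, among pregnancies still ongoing at the index gestational age, with follow-up as in Table 7.

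Do not delete the whole list of examples. In the third-dose section one phrase covers preterm birth and small size for gestational age together, so it must be split. The singleton, infant-linked live-birth restriction stays for small size for gestational age and major congenital malformations, as Table 3 has it.

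If the sponsor wants stillbirth among 20-week survivors or preterm birth among live births, keep each as a labelled sensitivity analysis and state what it estimates.

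The cost is one sentence in each of two sections, with no new data. Dropping the extra subsets would reduce the number of matching runs.

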8.7.3. Sensitivity analysis

8.7.3.1. Exposure misclassification

During the early stages of the roll out of COVID-19 vaccines, many vaccinations may have occurred outside traditional medical care settings without reimbursement from health insurers. The potential for lack of recording of COVID-19 vaccines in claims and electronic health records may lead to misclassification of exposed individuals as "unexposed" individuals, which will underestimate vaccine coverage rates and bias comparative risk estimates for the cohort design with concurrent unexposed individuals as comparators. To address this potential bias in comparative risk estimates, sensitivity analysis will be performed using a SCRI design. Additional sensitivity analyses will incorporate a cohort design with historical unexposed comparators for pregnancy and birth outcomes.

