If COVID-19 vaccines are administered without reimbursement from health insurers, there is the potential that they will not be recorded in claims and electronic health records. This situation may lead to misclassification of truly exposed individuals as "unexposed" comparators, which will underestimate vaccine coverage rates and may bias comparative risk estimates for the cohort design with concurrent unexposed comparators. The completeness of exposure data will be assessed in monitoring analyses before the final analyses are conducted by comparing study data with publicly available estimates of vaccine coverage and/or estimates based on immunization registry data from select states (if available); if the coverage estimates differ meaningfully from the "benchmarking" estimates (based on to-be-defined criteria in the SAP), then modifications to the study approach may be considered. If this happens, the SCRI may be designated as the primary study designs and/or linkage to immunization registries may be considered if feasible.

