8.3.3.3. Subgroup analysis

Subgroup analysis will be conducted in the following age categories, as appropriate for safety events of interest: 0-4, 5-11, 12-17, 18-64, and 65 years and older.

In additional analyses, the following safety events will be studied among individuals of specific ages if sufficient numbers of exposures are identified within the following subgroups:

- Multisystem inflammatory syndrome in children: ages 0-4, 5-11, 12-17, and 18-20 years
- Convulsions: ages 0-4 years
- Kawasaki disease: ages 0-4 years
- Myocarditis/pericarditis: ages 0-4, 5-11, 12-17, 18-24, 25-29, 30-39, 40-49, 50-64, and 65 years and older

Additional subgroup analyses of myocarditis/pericarditis will be conducted by sex, age and age by sex together (in the above age categories), dose number, and calendar time. Additional subgroup analyses may be conducted for other specific safety events of interest that have signaled in other studies or vaccine safety surveillance systems. Additionally, analyses to identify risk factors for postvaccine outcomes will be conducted for myocarditis/pericarditis. These analyses will be described in the SAP.

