8.7.1. Descriptive analysis

Descriptive analysis will report on utilization of Pfizer-BioNTech original monovalent COVID-19 Vaccine during the overall study period and during the study period, stratified in 12-week increments (to assess vaccine uptake and patterns of exposure over time). The proportion of individuals receiving at least 1 dose, at least 2 doses, and at least 3 doses of Pfizer-BioNTech original monovalent COVID-19 Vaccine will be estimated within the overall study population, among individuals who are immunocompromised, among individuals with a history of COVID-19, and among pregnant women. If additional doses of Pfizer-BioNTech original monovalent COVID-19 Vaccine are authorized and available in the data sources, the proportion of individuals receiving additional doses (at least 4 doses, at least 5 doses, etc.) will also be described.

PFIZER CONFIDENTIAL CT24-WI-GL02-RF02 3.0 Non-Interventional Study Protocol Template For Secondary Data Collection Study 20-May-2021 Page 89 of 120 Among individuals who receive a second dose of Pfizer-BioNTech original monovalent COVID-19 Vaccine, the proportion of individuals will be reported by type of second dose of COVID-19 vaccine, and time between the first and second doses will be described within the overall study population, among pregnant women, among immunocompromised individuals, among individuals with a history of COVID-19, and stratified by age (6 months through 4 years and \geq 5 years). Among individuals who receive a third dose of Pfizer-BioNTech original monovalent COVID-19 Vaccine, the proportion of individuals will be reported by type of third dose of COVID-19 vaccine, and time between the second and third doses will be described within the overall study population, among pregnant women, among immunocompromised individuals, among individuals with a history of COVID-19 vaccine, and time between the second and third doses will be described within the overall study population, among pregnant women, among immunocompromised individuals, among individuals with a history of COVID-19, and stratified by age (6 months through 4 years and \geq 5 years).

Additionally, characteristics (i.e., demographics, comorbidities, and other potential covariates) of the matched and unmatched study cohorts will be shown in a table. No statistical tests are planned for this comparison, but the balance of variables in the matched cohorts will be assessed using standardized differences or other suitable methods.

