8.7.3.2. Self-controlled risk interval design

Sensitivity analyses incorporating a SCRI design will be implemented for outcomes with an acute onset and short risk intervals (i.e., risk intervals no longer than 42 days; specific outcomes to be indicated in the SAP) in the overall study population, in pregnant women, in immunocompromised individuals, and in individuals with a history of COVID-19. The SCRI design will not be considered for pregnancy safety outcomes. Only vaccinated individuals will be included in the SCRI analysis; the rate of a specific safety event in a post-vaccination risk interval will be compared with that in a control interval within the same individual.

For the primary series analysis, the risk interval will combine person-time in the risk intervals after the first dose, after the second dose, and after the third dose (if applicable).

PFIZER CONFIDENTIAL CT24-WI-GL02-RF02 3.0 Non-Interventional Study Protocol Template For Secondary Data Collection Study 20-May-2021 Page 96 of 120 The control interval will be outcome specific, with the duration and timing relative to vaccination specified in more detail in the SAP. Control intervals will be defined during specific periods following vaccination (up to a maximum of 183 days); to avoid bias due to healthy vaccinee effects, pre-vaccination periods will not be used. A washout period between the risk and control intervals may be incorporated for safety events for which the risk interval is not well characterized.

Because of the self-controlled nature of the design, bias of comparative risk estimates arising from differences in the distribution of time-constant confounding factors between vaccinated and unvaccinated individuals is avoided with the SCRI design. Furthermore, as the design only includes vaccinated individuals, it avoids the potential for misclassification of unexposed status due to incomplete capture of COVID-19 vaccinations in data from claims or electronic health records.

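### A calendar-time trend in the myocarditis/pericarditis RR, or in uptake, could partly reflect unrecorded vaccinations, and the protocol states no SCRI estimate or coverage benchmark by period

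*Protocol*

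**What the plan says.** Section 8.7.3.1 places the missing records in time: "During the early stages of the roll out of COVID-19 vaccines, many vaccinations may have occurred outside traditional medical care settings without reimbursement" from insurers. It gives the consequence as misclassification of vaccinated people as unexposed, "which will underestimate vaccine coverage rates and bias comparative risk estimates for the cohort design" with concurrent comparators.

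Section 8.3.3.3 then states that "subgroup analyses of myocarditis/pericarditis will be conducted by sex, age and age by sex together (in the above age categories), dose number, and calendar time". It does not name the design for this subgroup, but the concurrent-comparator cohort is the primary design (8.1) and supplies the comparative estimates (8.7.2.2). The amendment log (Section 4, Version 2.0) gives the reason for the calendar-time subgroup: a regulator asked that changing incidence after vaccination be taken into account. Section 8.7.1 reports uptake "stratified in 12-week increments (to assess vaccine uptake and patterns of exposure over time").

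Two safeguards bear on this. The SCRI sensitivity analysis (8.7.3.2) is planned "in the overall study population, in pregnant women, in immunocompromised individuals, and in individuals with a history of COVID-19"; calendar period is not mentioned. The completeness check (8.3.1) is made "by comparing study data with publicly available estimates of vaccine coverage and/or estimates based on immunization registry data from select states (if available"), again without mention of period, and the criteria for a meaningful difference are left to the SAP.

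**The concern.** Missed vaccinees sit in the unexposed group, but they do not all do the same harm. For an outcome with a risk window of days 1 to 21, a missed vaccinee raises the comparator rate only while inside that window. Someone vaccinated long before contributes ordinary background risk. The dilution therefore follows the pace of vaccination: it is larger when many people are being dosed and close to nil when few are. Poorer recording in the early months would add to it.

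A true RR that is constant and above 1 could then be reported as rising. That is the comparison the calendar-time subgroup invites a reader to make, and the plan as written supplies no estimate in the same strata that is free of this dilution. For uptake the mechanism is simpler. Recorded uptake is true uptake times capture, so improving capture looks like rising uptake.

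**Working it through.** **The plan's own figure.** Section 8.5 gives a 92% probability that the upper 95% limit is below 2.5 for myocarditis/pericarditis, with 5,000,000 vaccinated, 2 doses each, 10 per 100,000 person-years, a 21-day window, 1:1 person-time and true RR 1.4.
- Comparator events: 5,000,000 × 2 × (21/365.25) × 10/100,000 = 57.5. Exposed events: 57.5 × 1.4 = 80.5.
- SE(log RR) = √(1/57.5 + 1/80.5) = 0.1727.
- Φ(ln(2.5/1.4)/0.1727 − 1.96) = 0.919.

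The figure reproduces, and this point does not alter it. It confirms the 21-day, two-dose setting used below.

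**Dilution formula.** Let q be the share of comparator person-time that truly lies in an unrecorded post-dose window. The comparator rate is multiplied by 1 + q(RR − 1), so

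RR seen = RR / (1 + q(RR − 1)).

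The protocol gives no value for q, for capture, or for uptake by period. All are assumptions here.

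**Plausible q.** With share h of the population starting vaccination per month, share u of doses unrecorded, two 21-day windows (42 days), and share U of the population recorded as unexposed: q = h × u × (42/30.4) / U.
- Early, h = 0.10, u = 0.40, U = 0.9 to 0.7: q = 0.061 to 0.079.
- Late, h = 0.01, u = 0.05, U = 0.9 to 0.7: q = 0.0008 to 0.001.

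A second route holds capture constant. The missed share of comparators is m = coverage × (1 − capture) / (1 − coverage × capture), and q = m × share in window.
- Early, coverage 50%, capture 70%, 45% in window: m = 0.15/0.65 = 0.231, q = 0.104.
- Late, coverage 70%, capture 70%, 2% in window: m = 0.21/0.51 = 0.412, q = 0.008.

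The 45% is high: it puts 0.50 × 0.45 = 22.5% of the whole population in a window at once. I therefore take 0.05 to 0.10 as the early range and near 0 as late.

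**Plausible RR on a 21-day window.** Section 6 quotes 7-day rate ratios of 10.0 (any mRNA vaccine, ages 12 to 39; 95% CI 2.9 to 46.5) and 2.4 (this vaccine; 95% CI 0.4 to 24.9). If the whole excess falls within 7 days (an assumption; Section 6 reports clustering at days 0 to 5):
- (7 × 10 + 14 × 1)/21 = 4.0
- (7 × 2.4 + 14 × 1)/21 = 1.47

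**Result.**

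| True 21-day RR | Seen, q = 0.05 | Seen, q = 0.10 | Seen, q = 0.001 |
|---|---|---|---|
| 4.0 | 4/1.15 = 3.48 | 4/1.30 = 3.08 | 4/1.003 = 3.99 |
| 1.5 | 1.5/1.025 = 1.46 | 1.5/1.05 = 1.43 | 1.50 |
| 1.4 | 1.4/1.02 = 1.37 | 1.4/1.04 = 1.35 | 1.40 |
| 1.0 | 1.00 | 1.00 | 1.00 |

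At the constant-capture values, an RR of 4 is seen as 4/1.311 = 3.05 early and 4/1.025 = 3.90 late. Drift appears even though capture never changes.

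**Uptake.** If true uptake is flat and capture rises from 0.80 to 0.95 (assumed), recorded uptake rises 0.95/0.80 = 1.19-fold. From 0.60 to 0.95 it rises 1.58-fold.

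**The case against.** The strongest reply is that this reads silence as error. The benchmark criteria are expressly deferred to the SAP, as are the SCRI outcomes and control intervals, and strata for a sensitivity analysis are ordinary SAP content. The list in 8.7.3.2 names populations and does not exclude calendar time. That stands in part: a reader might infer that no period-specific check will be done, and the protocol alone cannot show that. What it shows is that the calendar-time subgroup is promised and the matching check is not.

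Further, if exposure data prove incomplete, the SCRI may become the primary design or registries may be linked (8.1, 8.3.1, 8.9), and registry data are used where linkages already exist (8.3.1). This stands too. But the switch is discretionary, and a benchmark taken over the whole period could look acceptable while one period is poor.

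Incidence among recorded vaccinees (8.7.2.1) does not use the comparator, so a question about incidence alone escapes this dilution. The RR by calendar time does not.

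The protocol also discloses that missed doses understate coverage. Disclosure covers the level of uptake; it does not tell a reader how far a trend is real.

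Finally, the SCRI has weaknesses of its own for a calendar trend. Its control time is post-vaccination only, up to 183 days, and it removes only time-constant confounding, so seasonal change can enter. This stands, and it is why the SCRI should sit beside the cohort RRs and not replace them.

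**Conclusion.** The point holds in a limited form and calls for a cheap improvement. The protocol names an early-period recording problem, says that it biases the cohort RR, and plans two time trends exposed to it without stating a check by period. Under assumed q of 0.05 to 0.10 early and near 0 late, a constant 21-day RR of 4 would seem to rise from about 3.1–3.5 to nearly 4. An RR of 1.4 to 1.5 would shift by less than 0.1, and an RR of 1 not at all.

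Three stronger readings are not supported:
- That capture is known to be poorest early. Section 8.7.3.1 says only that it may be, and gives no rates. The RR drift does not need this; the uptake drift does need capture to change.
- That the RR must move by construction. It needs a true RR different from 1 and unrecorded doses inside the window.
- That an RR of 10 is at stake in the main analysis. That figure in Section 6 is a 7-day ratio for any mRNA vaccine at ages 12 to 39, and the main window is 21 days.

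**What to change.** In 8.7.3.2, add that the myocarditis/pericarditis SCRI will also be run in the calendar-time strata used for the cohort subgroup, and reported beside the cohort RRs before any trend is interpreted. State that it is a check, that its intervals will be wider within strata, and that its post-vaccination control time may carry seasonality.

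In 8.3.1 and 8.7.1, state that the coverage benchmark will be made by the same 12-week increments as the uptake series and shown with it.

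Both parts are needed. The benchmark shows whether recorded uptake tracks true uptake, but it would not by itself reveal RR drift that arises from the pace of vaccination under constant capture; the SCRI addresses that. The cost is extra strata in analyses already planned, with less precision in each.
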